15.0 Other Approvals

15.1 *Describe any approvals that will be obtained prior to commencing the research (e.g., school, external site, funding agency, laboratory, radiation safety, or biosafety).*

Response:

N/A: This study does not require any other approvals.

16.0 Provisions to Protect the Privacy Interests of Subjects

16.1 *Describe how you will protect subjects' privacy interests during the course of this research.*

NOTE: Privacy refers to an individual's right to control access to him or herself. Privacy applies to the person. Confidentiality refers to how data collected about individuals for the research will be protected by the researcher from release. Confidentiality applies to the data.

Examples of appropriate responses include: "participant only meets with a study coordinator in a classroom setting where no one can overhear", or "the participant is reminded that they are free to refuse to answer any questions that they do not feel comfortable answering."

Response:

Subject will be recruited at a private patient's room in the ED where no other people are around beside the patient, their legal guardian, and the RN who performs the needle stick.

16.2 *Indicate how the research team is permitted to access any sources of information about the subjects.*

*NOTE: Examples of appropriate responses include: school permission for review of records, consent of the subject, HIPAA waiver. This question **does apply** to records reviews.*

Response:

The PI and her mentors are physicians at the children's hospital, they have been granted with the right to access the electronic power chart system by Kaleida Health IST to carry out their duties as physicians. The research personnel also are granted with the right to access the power chart by Kaleida Health IST for carrying out their duties as researcher staff.

In order to screen potential eligible patient for this study, we will also apply for a partial HIPAA waiver from our IRB.

17.0 Data Management and Analysis

17.1 *Describe the data analysis plan, including any statistical procedures. This section applies to both quantitative and qualitative analysis.*

Response:

All data analyses will be performed with SAS (version 9.2; SAS Institute, Inc., Cary, NC) and R (version 3.0.3) software. Chi-square and Fisher's exact test will be used to compare adverse events (e.g., systemic reaction, anaphylaxis, SOB, dyspnea, excess bleeding or hematoma formation), venipuncture and catheterization first attempt success, and number of patients with no to mild pain during needle insertion.

The Kruskal-Wallis test will be used to compare each of the two observers' assigned scores on the PBCL across three time periods: pre, procedure and post-procedure. Pre-procedure is defined as the time period prior to needle insertion including the placement of Vapocoolant, pain control or sham device up to needle insertion. The procedure period is defined as needle insertion through withdrawal. Post-procedure is defined as the 2 minute time period after needle withdrawal. Only patient and observer pain scores will be used for first-time needle insertion. If first attempt is failed, subject will be withdrawn from the study. Comparisons of pain scores of the five intervention groups to placebo (sham device) will be analyzed via ANOVA.

17.2 If applicable, provide a power analysis.

NOTE: This may not apply to certain types of studies, including chart/records reviews, survey studies, or observational studies. This question is asked to elicit whether the investigator has an adequate sample size to achieve the study objectives and justify a conclusion.

Response:

For chi-square analysis, based on a medium effect size of 0.3, alpha of 0.05, degree of freedom of 8, and 80% power it is estimated we will need a total of 168 subjects (56 per group). (*QFAB Bioinformatics*. 2015)

17.3 Describe any procedures that will be used for quality control of collected data.

Response:

Our RA will double check the data form to assure accuracy and completeness of data collection, if there is any missed data point, the RA will fill in the missing information immediately.

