1.0 Objectives

1.1 Describe the purpose, specific aims, or objectives of this research.

Response:

The purpose of this study is to compare the anxiety and pain levels of patients when using Buzzy with ice wings, Vapocoolant, and placebo during venipuncture procedure in pediatric patients.

1.2 State the hypotheses to be tested, if applicable.

NOTE: A hypothesis is a specific, testable prediction about what you expect to happen in your study that corresponds with your above listed objectives.

Response:

We hypothesize that the Buzzy will provide greater pain relief based on patient self-report and parent report of their child's pain as well as independent observation when compared to Vapocoolant or placebo.

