The Procedure Behavior Checklist (PBCL) is a well-established observational pain measure that has been validated for children 3-18 years old. It evaluates both the intensity and frequency of 10 defined behaviors that indicate distress. The PBCL was developed by Katz et al in 1980. On a scale of 1-5, it rates child's muscle tension, screaming, crying, restraint needed, verbalized pain, anxiety, etc. The scores are then added together to give a final score. The Faces Pain Scale – Revised (FPS- R; Hicks et al 1990) is a self-report measure used to assess the intensity of children's pain. It consists of 6 faces, with each one representing an increasing degree of pain moving from left to right in increments of two starting from zero (0, 2, 4, 6, ,8, 10).

Both of the PBCL and Faces pain scale –revised have been validated tool and used frequently in clinical practices and studies when evaluate patient's pain scale.

In this study, we will compare the effectiveness of pain release devices i.e. buzzy, with vapocoolants or placebo. We will use the validated PBCL and Faces pain scale-revised methods as the pain evaluation tools. To our knowledge, no study has been performed on comparison of the effectiveness of these commonly used pain release devices. We hope to contribute some useful information in this field through our research.

3.2 *Include complete citations or references.*

Response:

*Blount R. L., Zempsky W. T., Jaaniste T., Evans S., Cohen L. L., Devine K. A., Zeltzer L. K. Management of pain and distress due to medical procedures. In: Roberts M C, Steele R, editors. *Handbook of pediatric psychology*. 4th Ed. New York: Guilford Press; 2009. pp.171–188.*

Cohen Reis E. & Holubkov R. (1997). Vapocoolant spray is equally effective as EMLA cream in reducing immunization pain in school-aged children. Pediatrics, 100 (6).

Hamilton J.G. (1995). Needle phobia: A neglected diagnosis. Journal of Family Practice, 41 (2):169-175.

Hicks C.L., von Baeyer, C.L., Spafford P.A., van Korlaar I. & Goodenough B. The Faces Pain Scale - Revised: toward a common metric in pediatric pain measurement. Pain 93(2001) 173-183.

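### The only test that names the PBCL compares time periods within the same child, not arms, so as written it does not test the between-arm hypothesis

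*Combined protocol and SAP*

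**What the plan says.** Section 17.1, repeated under the Data Management and Analysis heading at the end of the document, gives this rule for the PBCL: "The Kruskal-Wallis test will be used to compare each of the two observers' assigned scores on the PBCL across three time periods". The periods are then defined. The pre-procedure period runs up to needle insertion, "including the placement of Vapocoolant, pain control or sham device up to needle insertion". The procedure period runs from insertion to withdrawal. For the third, "Post-procedure is defined as the 2 minute time period after needle withdrawal". Neither the rule nor these definitions say that arms are compared.

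Two further sentences in 17.1 bear on the point: "Only patient and observer pain scores will be used for first-time needle insertion", and then "Comparisons of pain scores of the five intervention groups to placebo (sham device) will be analyzed via ANOVA". The chi-square and Fisher tests cover adverse events, first-attempt success and the number of children with no to mild pain. They do not name the PBCL.

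The hypothesis in section 1.2 is between arms. It covers self-report and parent report "as well as independent observation when compared to Vapocoolant or placebo". Section 2.1 also states the primary outcome as Buzzy against vapocoolant or placebo, on anxiety and pain. Section 3.1 says the PBCL "is a well-established observational pain measure", and that "it rates child's muscle tension, screaming, crying, restraint needed, verbalized pain, anxiety". Section 10.1 has two physicians score the video and takes the mean of their scores when they differ.

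**The concern.** The PBCL carries the independent-observation part of the hypothesis. It is also the only listed instrument that the background describes as rating anxiety, and the trial is open label, so the video score matters. Yet the one test assigned to it by name asks whether distress differs before, during and after the needle. That can be answered yes when the three treatments are identical, or no when Buzzy is better throughout.

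The method does not suit the time question either. Kruskal-Wallis assumes independent groups, and by the definitions in 17.1 the periods are consecutive phases of one child's procedure. At stake is whether the plan contains any PBCL result that bears on the arms and was fixed before the data are seen.

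**Working it through.** **The plan's own figure.** Section 17.2 sizes the trial for a chi-square test with w = 0.3, 8 df, alpha 0.05 and 80% power. The noncentrality is N·w². At N = 168 this is 168 × 0.09 = 15.12, and power is 80.3%. The smallest N that reaches 80% is 167, which three equal arms round up to 168. The figure reproduces, but it does not size any PBCL comparison.

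**The passages side by side.**

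| | Hypothesis (1.2, 2.1) | PBCL test (17.1) | ANOVA (17.1) |
|---|---|---|---|
| Factor | arm | time period | intervention group versus placebo |
| Groups | 3 arms | 3 periods of one child | five plus placebo, in a three-arm trial |
| Score | independent observation among others | PBCL, each observer | pain scores, instrument not named |
| Buzzy vs vapocoolant | required | no | no |

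**Effect of ignoring the pairing.** With no time effect and within-child correlation ρ, differences between period means have variance proportional to (1 − ρ), but the test assumes 1. Its statistic then behaves roughly like (1 − ρ) times a chi-square with 2 df. For 2 df, P(χ² > x) = exp(−x/2), so the 5% critical value is −2 ln 0.05 = 5.991. The true rejection rate is about exp(−5.991 / [2(1 − ρ)]):

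- ρ = 0.3: exp(−4.279) = 1.4% (simulated 1.5%)
- ρ = 0.5: exp(−5.991) = 0.25% (simulated 0.2 to 0.4%)

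So even for a time question the nominal 5% is not held.

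**Simulation.** The documents give 56 per arm, three periods and alpha 0.05. The following are assumptions: normal scores, ρ = 0.5, and a time effect that shifts only the procedure period. There were 3,000 trials per cell in the main grid. The 1 SD row comes from supplementary runs of at least 2,000 per cell.

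| Time effect (SD) | As written, identical arms | As written, Buzzy 0.5 SD better in all periods |
|---|---|---|
| 0 | about 0.3% | about 0.3% |
| 0.1 | 4.6% | 3.5% |
| 0.25 | 63% | 58% |
| 0.5 | 100% | 100% |
| 1 | 100% | 100% |

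The two columns are nearly the same: whether Buzzy works makes almost no difference. On the same data, Kruskal-Wallis by arm on the procedure score rejects in about 5% with identical arms and about 75% with the benefit, at every time effect.

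**Sensitivity.** With ρ = 0.3 and 0.7, identical arms and a 0.5 SD time effect give 99.9% and 100%. The all-period benefit with no time effect gives 1.4% and 0.1%. PBCL-like totals (ten items scored 1 to 5, 17% or 36% of children at the minimum) give 99.8 to 99.9% and 0.6 to 0.8% in the same two cells. By arm they give about 5% and 59 to 65%.

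**A limit.** A benefit confined to the procedure period does reach the test, but only by shifting the pooled procedure mean. A 0.5 SD benefit in one arm of three moves it by 0.5/3 = 0.17 SD, against any rise in distress. Rejection is 19% with no time effect and 2.3% at 0.25 SD, where identical arms give 63%. A real benefit can therefore lower the rejection rate.

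**The case against.** Kruskal-Wallis is an independent-groups test, the trial has three arms, and the pre-procedure definition mentions the interventions. The authors may well have meant a comparison of arms at each of three periods. That is plausible, but the sentence does not say it. It would also yield 3 periods × 2 observers = 6 tests with none designated, and testing each observer separately conflicts with the mean-score rule in section 10.1.

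A reader might infer that no between-arm PBCL test is planned at all. The documents do not support that. Section 17.1 speaks of observer pain scores just before the ANOVA sentence, and section 3.1 calls the PBCL a pain measure, so the ANOVA may be meant to include it. What stands is that the ANOVA names no instrument, period or observer rule, counts five intervention groups in a three-arm trial, and compares only with placebo.

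A reader might also infer that the test would almost never be significant when Buzzy is better in every period. That holds only for a time effect of about 0.1 SD or less. The documents give no time effect, and nothing in them suggests that a needle stick barely changes distress.

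Nor does the plan say that a significant period test would be read as Buzzy superiority. Rejecting when distress really changes is the right answer to a time question; the fault is that the hypothesis asks a different one. Finally, section 2.1 designates no instrument, so the PBCL is not a named primary measure. It is still part of the stated hypothesis.

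**Conclusion.** The point holds for the text as written: the one named PBCL test has time as its factor, is applied to repeated measures, and does not compare the arms. The later ANOVA does not reliably repair this. Following the rule literally gives a PBCL result that is invalid for time and uninformative about arm, so it should be corrected before analysis.

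That the three scores belong to one child is an inference, but it follows directly from the period definitions. The percentages rest on assumed score distributions, correlations and time effects and are illustrative. The conclusion that a test by period is not a test of arms needs none of them. The sample size of 168 is not affected.

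**What to change.** Replace the Kruskal-Wallis sentence, in both places, with:

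*The mean of the two observers' PBCL scores for one named period (for example the procedure period) is compared among the three arms by Kruskal-Wallis with arm as the factor, at two-sided alpha 0.05. If this is significant, Buzzy vs vapocoolant and Buzzy vs placebo are compared by Wilcoxon rank-sum tests, each at 0.05.*

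The procedure period is only a suggestion, made because the pre-procedure period already includes placement of the intervention and so is not an untreated baseline. The authors may choose another period but must name one. Since section 2.1 speaks of reduction, they should also say that it is judged as the difference between randomised arms, or define it otherwise.

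Simulated under the same normal model (4,000 trials), this rule makes a false pairwise claim in 4.6% of trials with equal arms. When Buzzy equals vapocoolant and both beat placebo by 0.5 SD, it makes a false Buzzy-versus-vapocoolant claim in 5.1%. If Buzzy is 0.5 SD better than both, power is 74% overall and 65 to 66% for each pair.

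If only one score per subject is collected, as section 18.1 A suggests, apply the rule to that score and describe it as a whole-tape score, not a procedure-period score. Treat other periods as secondary. If time is analysed, use a repeated-measures model with arm, period, arm-by-period and a child effect. State whether the ANOVA covers the PBCL, so that one between-arm PBCL test is designated.

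The cost is wording only if one score per child is used; period scores require the observers to score each period. Two separate points also need reconciling: the count of five intervention groups, and the end of taping at completion of venipuncture (section 10.1) against the 2-minute post-procedure period (17.1). Keeping that period would mean longer taping.

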10.0 Procedures Involved

10.1 Provide a description of all research procedures or activities being performed and when they are performed once a subject is screened and determined to be eligible. Provide as much detail as possible.

NOTE: This should serve as a blueprint for your study and include enough detail so that another investigator could pick up your protocol and replicate the research. For studies that have multiple or complex visits or procedures, consider the addition of a schedule of events table in in your response.

Response:

Randomization of subject into one of the three study arms

There will be three arms of this study with each arm testing a different pain reducer: Buzzy Bee, Vapocoolant, and placebo. We will use a sham device e.g. a band around the arm for placebo control.

After obtaining informed consent, the patients will be randomized into one of the three groups following a randomization table created by a statistician. Whichever intervention is randomly selected will be performed on patient prior to the needle stick.

These methods have been used in the ED as part of routine procedures to help patient for pain relief from a needle stick, the RNs are familiar with these methods. However, for the purpose of this study, the training videos will be uploaded in the Kaleidoscope Talent management for RNs to review the procedure and help them to refresh their memories.

Videotaping of subject

Using a camera, an ED research assistant will videotape subject's whole body including the facial expression while phlebotomy and IV catheter placement is performed for scoring of the PBCL. We will tape the entire venipuncture procedure starting from sterilization and ending at the time when the venipuncture is completed. If the first venipuncture procedure attempt is failed, we will not tape the second attempt. This subject will be withdrawn from the study.

Obtaining pain scores from subject and legal guardian using the Faces Pain Scale-Revised instrument

Before and after the venipuncture procedure, we will ask the legal guardian and subject to complete a Faces pain scale revised form. Since the revised form is validated to use for both adult and children, the same document will be used for the legal guardian and children for this study. This document is attached with this submission.

Reviewing of the videotape

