Two physicians will review the video tape independently, and give a score using the PBCL tool. These two physicians are blinded to the study aims. They will be trained on how to use the PBCL by the PI.

In the event when there is a discrepancy of the PBCL score between the two reviewers, the mean of the two scores will be used as the final score.

10.2 Describe what data will be collected.

NOTE: For studies with multiple data collection points or long-term follow up, consider the addition of a schedule or table in your response.

Response:

We will collect demographic data, reason for venipuncture, PBCL score, facial pain score etc.

10.3 List any instruments or measurement tools used to collect data (e.g. questionnaire, interview guide, validated instrument, data collection form).

Include copies of these documents with your submission.

Response:

The following documents will be used for data collection:

1. Data collection form

2. Procedure behavior check list (PBCL)
3. The Faces Pain scale-revised document.

These documents will be submitted with this IRB application.

10.4 Describe any source records that will be used to collect data about subjects (e.g. school records, electronic medical records).

Response:

Kaleida health Electronic power chart records will be used for data collection.

*10.5 Indicate whether or not **individual** subject results, such as results of investigational diagnostic tests, genetic tests, or incidental findings will be shared with subjects or others (e.g., the subject's primary care physician) and if so, describe how these will be shared.*

Response:

No individual subject results will be shared with the subject or others.

*10.6 Indicate whether or not **study** results will be shared with subjects or others, and if so, describe how these will be shared.*

Response:

Study results will not be shared with subjects or others. The final results of this study may be presented at a conference or published in a peer reviewed journal; however, only group data will be publicized in these circumstances, no individual identifiable information will be released.

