18.0 Confidentiality

A. Confidentiality of Study Data

Describe the local procedures for maintenance of confidentiality of study data and any records that will be reviewed for data collection.

18.1 A. Where and how will all data and records be stored? Include information about: password protection, encryption, physical controls, authorization of access, and

*separation of identifiers and data, as applicable. Include physical (e.g. paper) **and** electronic files.*

Response:

Completed paper data form with subject identifier and signed consent/assent documents will be placed in a locked study box in the ED. The study coordinator will collect these documents on a daily basis. The documents will be stored in a locked file cabinet in a research storage room (Conventus, Room 5201, [name]). Each subject's data form will be labeled with a unique study identify number (ID). In addition, we will use a "**subject enrollment log**" to track subject's enrollment and data entry status. This log is attached with this submission. Subject's ID, medical record number, enrollment date, and data entry date will be entered in this log. This log will be stored in a locked file cabinet in the study coordinators' office Room 5201 in the Conventus building.

The data will be entered in a Microsoft excel spread sheet (**Database**) by a trained research assistant. Database will be saved in a password protected UPA secure online drive. No subject's name, DOB, medical record number or Fin Number will be entered in the database. The study ID number will be served as the code key to link the Database and the Subject enrollment log. We need to collect subject's medical record number for the purpose of answering query.

The study coordinator will transfer the subject's video from the camera to a password protected secure UPA online folder, which will also be shared with the two physicians who will reviewed these videos. Then the coordinator will erase the video from the camera.

The two trained physician observers will review the video saved on the password protected secure online folder at their Conventus offices and give a PSCL score for each subject. Video will be erased upon completing the study.

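### The scoring section makes the two-reviewer mean the final PBCL score, but the analysis plan tests each reviewer separately in three periods, with no rule for which result counts

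*Combined protocol and SAP*

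**What the plan says.** Three parts of the plan describe the PBCL score.

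- **Scoring.** Section 3.1 describes the instrument as a set of rated behaviours: "The scores are then added together to give a final score". Section 10.1 has two physicians score each video independently and, where they differ, "the mean of the two scores will be used as the final score". Section 18.1 A, on data handling, has the observers "give a PSCL score for each subject" (the abbreviation is evidently a slip for PBCL). Neither 10.1 nor 18.1 A mentions scoring by period.
- **Analysis.** Section 17.1, repeated in the unnumbered Data Management and Analysis text after section 32, uses Kruskal-Wallis to "compare each of the two observers' assigned scores on the PBCL across three time periods". The periods are pre-procedure, procedure and post-procedure. The averaged score is not named in this or any other analysis.
- **Role.** Observation is one of three supports of the hypothesis in 1.2, beside the child's and the parent's reports: "as well as independent observation when compared to Vapocoolant or placebo".

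**The concern.** The variable that 10.1 defines as final is not the one that 17.1 names for testing. Someone working from 17.1 obtains a result for each observer in each period. If one observer's scores favour Buzzy and the other's do not, the plan has no rule to decide between them, and the choice could be made after the results are seen. Each of those tests also uses one rater's score although the protocol already provides for a mean.

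There is a practical risk as well. The period definitions appear only in the analysis text. If the reviewers recorded one score per video, the period analysis could not be done. Sections 18.1 A and 18.2 A have the videos erased at the end of the study, so the missing scores could not be recovered after that.

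**Working it through.** **1. The plan's own figure.** The only computed figure is the total of 168 in 17.2, for a chi-square test with effect size 0.3, 8 degrees of freedom, alpha 0.05 and 80% power. With noncentrality N × 0.3², the smallest N is 167, and power at 168 is 80.3%, so the figure reproduces. It does not concern the PBCL, and the plan gives no power figure for that endpoint.

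**2. Counting the variables.**

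| Source | PBCL variable |
|---|---|
| 10.1 | Final score = mean of two reviewers (if they agree, the mean equals the common score) |
| 17.1 and end text | 2 observers × 3 periods = 6 variables per child |
| 10.1 mean applied within the 17.1 periods | 3 variables per child |

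With every test at 0.05 and treated as independent, the chance of at least one false positive is 1 − 0.95⁶ = 26.5% for six tests and 1 − 0.95³ = 14.3% for three. These tests would be positively correlated, so the true chances would be lower.

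**3. Two observers against their mean, in one period.** Assumed, because the documents give none of it: the test compares arms; the inter-rater correlation r is 0.6 to 0.9; the raters have equal variance; each observer's test has 80% power. Formulas:

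- Reliability of the mean: 2r/(1+r).
- Variance of the mean relative to one rater: (1+r)/2.
- Power with the mean: Φ(2.80/√((1+r)/2) − 1.96), where 2.80 = 1.96 + 0.84.
- At least one false positive, and disagreement on significance: bivariate normal with correlation r, two-sided 0.05.

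| r | Reliability of mean | Relative variance | Power with mean | At least one false positive | Observers disagree |
|---|---|---|---|---|---|
| 0.6 | 0.75 | 0.80 | 88% | 8.8% | 20% |
| 0.7 | 0.82 | 0.85 | 86% | 8.3% | 17% |
| 0.8 | 0.89 | 0.90 | 84% | 7.8% | 14% |
| 0.9 | 0.95 | 0.95 | 82% | 7.0% | 10% |

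Worked line for r = 0.6: √0.80 = 0.894; 2.80/0.894 = 3.13; 3.13 − 1.96 = 1.17; Φ(1.17) = 0.88.

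**4. Check with the planned test.** Kruskal-Wallis was simulated on three arms of 56 with normal scores, 10,000 runs per setting and r from 0.6 to 0.9. With no true effect, at least one observer was significant in 8.7% to 7.2% of trials. With one arm shifted by 0.45 SD (assumed), the observers disagreed in 28% to 15% of trials; with 0.6 SD, in 13% to 7%. A single test on the mean was falsely positive in 4.6% to 5.4%.

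**5. Recording against the periods.** Section 17.1 says "Post-procedure is defined as the 2 minute time period after needle withdrawal". Section 10.1 has the video "starting from sterilization and ending at the time when the venipuncture is completed". On that wording the post-procedure score has no footage, whichever aggregation rule is used.

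**The case against.** Four points can be made on the other side.

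- **The mean may be used after all.** A reader might infer that the averaged score is discarded. The documents do not establish that. Section 17.1 also says "Comparisons of pain scores of the five intervention groups to placebo (sham device) will be analyzed via ANOVA", and 3.1 presents the PBCL as a pain measure, so the mean could enter that ANOVA. This stands: what can be said is that no analysis names it. If the ANOVA did use it, the same instrument would be analysed in two ways, again with no rule for which leads.
- **Period scores may exist.** A reader might infer that reviewers give one score for the whole video, so that needle insertion cannot be separated from skin preparation and device placement. The documents do not settle this. Section 10.1 does not say what span a score covers, 18.1 A concerns file handling, and the PBCL form, submitted separately, may already have period columns. The defect is that 10.1 is silent on periods, not that period scores will be absent.
- **The figures rest on a reading.** The Kruskal-Wallis sentence can be taken as comparing periods with each other rather than arms. On that reading the error rates and power above do not describe a treatment comparison. This also stands.
- **The PBCL is not named as the primary instrument.** Section 2.1 names none. That limits the weight of the point but does not remove the contradiction.

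**Conclusion.** The plan contradicts itself on the observer endpoint. Section 10.1 defines a two-reviewer mean as final, while 17.1 and the end text test each observer separately in periods that 10.1 does not mention. That much rests on the text alone and is secure.

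The size is illustrative. For one period, under the assumptions in the working, there is about a 7% to 9% chance of at least one false positive and a 10% to 20% chance of conflicting observer results (7% to 28% under the other assumed effects). Using the mean would raise power from 80% to about 82% to 88% with the same children and reviewers. These figures should not be quoted as properties of this trial.

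Loss of the period analysis is a conditional risk: it follows only if reviewers record a single score per video. The point affects one of the three supports of the hypothesis and should be corrected before scoring begins.

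**What to change.** - **Section 10.1:** state that each reviewer scores the PBCL separately for each period defined in 17.1, and that the final score for a period is the mean of the two reviewers. Bring 18.1 A into line.
- **Section 17.1 and the end text:** replace the separate observer scores with the mean of the two observers' PBCL scores, compared between arms in each planned period. Keep the pre-procedure comparison, since by the plan's own definition it covers placement of the vapocoolant or device.
- **Observer-specific scores:** use them only to report agreement, as an intraclass correlation.
- **Post-procedure period:** reconcile its definition in 17.1 with the end of taping in 10.1.

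This cuts the PBCL tests from six to three. It does not say which of the three periods leads; that would need its own statement. The cost is wording, a score sheet with a column per period if the form lacks one, and slightly longer scoring per video. No extra children or reviewers are needed.
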